Rationale for using cardiac MRI to measure cardiac hemodynamic parameters

One way to measure the short term impact of any therapy on the cardiovascular system is with cardiac magnetic resonance imaging (MRI), which has been shown to be sensitive in measuring RV hemodynamic parameters. Furthermore, cardiac MRI findings correlate with clinical changes and can have prognostic value in PH. Compared to standard, 2–dimensional echocardiography, cardiac MRI has been shown to be superior in detecting regional wall motion abnormalities, RV function, size and muscle mass. Cardiac MRI also offers advantages over echocardiography since obesity or emphysema do not interfere with the MRI image quality and thus interpretation. A recent pilot study using cardiac MRI demonstrated RV remodeling in overlap syndrome patients compared with COPD patients, further confirming the utility of this modality. Another pilot study detects early fibrosis changes of extracellular volume (ECV) mapping techniques in COPD patients. Thus, we believe that cardiac MRI may be the preferred technique to assess pulmonary hemodynamics and RV function in patients with COPD and OSA overlap syndrome.

Overlap Syndrome and Upper Airway Inflammation

Obstructive sleep apnea is characterized by a recurrent collapse of the upper airway which has been shown to be associated with an increase inflammatory cells in surgical samples from the uvula, pharyngeal and nasal mucosa, and upper airway muscle. COPD is also characterized chronic inflammation of upper and lower airways, which was initially triggered by smoking. Since recent evidence demonstrated that exacerbation of COPD is associated with increased inflammation of both upper and lower airways, upper airway inflammation from OSA in patients with overlap syndrome (coexistence of OSA and COPD) may contribute to worse COPD prognosis comparing to patients with COPD alone. However, there is limited research in upper airway inflammation of patients with overlap syndrome at present time and more research is warranted. A minimally invasive technique, pharyngeal lavage, has been recently developed to assess mucosal inflammation of the upper airways in normal, OSA, and heavy snoring patients. With this new technique, we believe that we could further characterize the upper airway inflammation and potential pathophysiology in patients with overlap syndrome.

Positive airway pressure therapy in COPD

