9. RESEARCH DESIGN AND METHODS

Part One Study Objective: The first part is a cross-sectional cohort study comparing subjects with overlap syndrome to those with COPD alone and those with OSA alone.

Subjects: Our target sample will be 150 subjects in the overlap syndrome group. This group will include subjects with age > 18 years with known or suspected diagnosis of overlap syndrome, which we will define as COPD: Global Obstructive Lung Disease (GOLD) stage 2 disease or higher and OSA: apnea-hypopnea index (AHI) >15/hour. We will exclude patients already using oxygen or BiLevel/CPAP, patients with known or suspected renal failure (creatinine >1.5 mg/dl), pregnant women (due to possible risk to the fetus due to cardiac MRI and gadolinium contrast), patients with atrial fibrillation or frequent (>10/h) premature ventricular contractions (since these may complicate cardiac MRI sequences) and patients with known contraindications to

MRI: metallic (ferromagnetic) implants, cardiac pacemakers, past history of claustrophobia.

The control subjects will be divided into two groups, one with COPD only (50 subjects) and the other with OSA only (50 subjects). The COPD control group will include subjects with known COPD diagnosed by a pulmonologist (GOLD stage 2 or higher). The OSA control group will include subjects with a known diagnosis of OSA diagnosed by a sleep specialist (apnea-hypopnea index, AHI >15/hour). The exclusion criteria for the control subjects will be the same as the overlap syndrome subjects.

Study enrollment: All patients will be recruited through the outpatient pulmonary and sleep medicine clinics at the UCSD hospitals. Poster advertisements will be placed in the outpatient clinics to encourage subject recruitment through physician referral. COPD patients in outpatient pulmonology clinics who express interest in enrolling in the study will be approached by one of the study investigators to obtain informed consent. COPD patients meeting eligibility criteria will be screened for OSA risk and scheduled for overnight polysomnography (PSG) as part of baseline visit. COPD patients with coexisting OSA will be enrolled in the overlap syndrome group. COPD patients without coexisting OSA will be enrolled in the COPD only control group. If COPD patients are referred for clinically indicated sleep studies, these patients will also be eligible for participation (as either COPD only or overlap syndrome patients), depending on the results of the sleep study.

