
Baseline visit: At the baseline visit, all 3 groups (overlap syndrome, COPD only and OSA only) will undergo a baseline PSG and measurement of body weight and height to calculate body mass index (BMI). Cardiac MRI will be done to measure RV and LV hemodynamics. Data regarding RV function with RVEDV (primary endpoint), RVESV, RVEF, RV mass index, right atrial pressure, PA pressure and blood flow, indices of RV geometry, thickness and interdependence, as well as LV function including LVEDV, LVESV, LVEF, LV mass index, LV wall motion, extracellular volume (ECV) and coronary blood flow will be collected. Phlebotomy will be done to take blood samples for complete blood cell counts (with differentials), renal profiles, venous gas analysis, and exploratory analyses of inflammatory biomarkers and cytokines (CRP, TNF-alpha, IL-6, P-selectin, ICAM-1). Overnight urine samples will be collected to measure catecholamine excretion levels (epinephrine, norepinephrine, metanephrine, normetanephrine). Endothelium function will be evaluated through the non-invasive finger probes of the EndoPAT 2000 device (Itamar Medical, Caesarea, Israel). EndoPAT device measures digital pulse amplitude with the probes placed on the tips of both index fingers in reaction to temporary occlusion of arterial blood flow (achieved by blowing up a blood pressure cuff around the arm) for 5 minutes. Assessment of exercise capacity will be done using six-minute-walk-distance (6MWD) test. Saint George Respiratory Questionnaire (SGRQ) score and SF-36 Questionnaire will be used to assess health-related quality of life (HRQOL). The modified Medical Research Council (MMRC) score will be used to assess severity of dyspnea. The Epworth Sleepiness Scale (ESS) and Pittsburg Sleep Quality Index (PSQI) will be used to assess sleep quality and relevant symptoms. Assessment of upper airway inflammation will be done with a minimally invasive technique, pharyngeal lavage, immediately before and after the sleep study. To collect pharyngeal lavage samples, subjects simply gargle 45 ml of sterile saline in 15 ml increments for 10 seconds, then spit the saline for collection and analysis. The pharyngeal lavage fluid will be used to analyze cell counts with differential and the remaining will be frozen for later analysis of inflammatory biomarkers. Assessment of cognitive function will be done using psychomotor vigilance task (PVT) and motor sequence task (MVT) by a computer program. Pulmonary function tests (PFTs) will be performed using the American Thoracic Society (ATS) criteria. BODE index (COPD mortality risk index predictor) will be calculated from these parameters listed above. The MRI will be scheduled as soon as available after the overnight sleep study. The time commitment for the sleep study will be 10 hours. The time commitment for the pulmonary function test will be 1 hour. The time commitment for the MRI is typically 30-40 minutes. In total, the time commitment to complete all of the required procedures of the Baseline Visit is approximately 12 hours.

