
Part Two Study Objective: The second part of the study is a prospective, parallel-group, randomized, controlled pilot study examining the effect of BiLevel therapy (and NOT if needed) vs. NOT alone in patients with overlap syndrome (20 subjects in each treatment arm).

Study Intervention: This will be done in 40 subjects in overlap syndrome group only who provide informed consent (20 subjects in each treatment arm). Randomization of overlap syndrome subjects to nocturnal BiLevel therapy (plus oxygen if needed based on saturations <88% while on stable bi-level settings), and NOT only will be done using sequentially-numbered, opaque, sealed envelopes using 1:1 allocation ratio. Regular therapy with COPD medications including long-acting anticholinergic medications and inhaled corticosteroids will be continued as advised by the treating pulmonologist. Only COPD subjects with stable clinical course during the duration of study intervention will be called for follow-up visits as any COPD exacerbations during the course of study intervention may potentially confound the follow-up study results. The time commitment for this initial visit will require up to 2-3 hours of the subjects time.

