Study endpoints: Primary endpoint: RVEDV (estimated by cardiac MRI) across the three study groups, and following intervention in the overlap syndrome patients in the randomized trial. Secondary endpoints: RVESV, RVEF, RV mass index, right atrial pressure, PA pressure and blood flow, indices of RV geometry, thickness and interdependence, LVEDV, LVESV, LVEF, LV wall motion, , extracellular volume, coronary blood flow, endothelial function (EndoPAT), serum complete blood cell counts (with differentials), serum renal profiles, pharyngeal lavage cell counts and differentials, serum and pharyngeal lavage inflammatory biomarkers (CRP, TNF-alpha, IL-6, P-selectin, ICAM-1), sympathetic activity (measured by urinary catecholamine excretion), HRQOL score and BODE index.

To offset transportation costs, parking costs and use of the volunteer's time, subjects will receive \$150.00 for the overnight sleep study and an additional \$100.00 for the MRI for a total of \$250.00 upon completion of all tests in Part I. Study staff might ask the subject to return for a second overnight sleep study visit in the event the

data is of poor signal quality or we were unable to obtain sufficient data to complete analysis. If the subject agrees to return for a repeat study, he/she will be compensated \$150.00 for their time and transportation.

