10. HUMAN SUBJECTS

We anticipate recruiting a total of 150 patients for phase one study: 50 patients with overlap syndrome, 50 patients with COPD, and 50 patients with OSA, age and gender matched to the overlap syndrome patients. For the phase two study, we aim to recruit 40 patients among the overlap syndrome patients who participated in phase one.

Phase One Study:

This group will include subjects with age > 18 years with known or suspected diagnosis of overlap syndrome, which we will define as COPD: Global Obstructive Lung Disease (GOLD) stage 2 disease or higher and OSA: apnea-hypopnea index (AHI) >15/hour. We will exclude patients already using oxygen or BiLevel/CPAP, patients with known or suspected renal failure (creatinine >1.5 mg/dl), pregnant women (due to possible risk to the fetus due to cardiac MRI and gadolinium contrast), patients with atrial fibrillation or frequent (>10/h) premature ventricular contractions (since these may complicate cardiac MRI sequences) and patients with known contraindications to MRI: metallic (ferromagnetic) implants, cardiac pacemakers, past history of claustrophobia. The control subjects will be divided into two groups, one with COPD only (50 subjects) and the other with OSA only (50 subjects). The COPD control group will include subjects with known COPD diagnosed by a pulmonologist (GOLD stage 2 or higher). The OSA control group will include subjects with a known diagnosis of OSA diagnosed by a sleep specialist (apnea-hypopnea index, AHI >15/hour). The exclusion criteria for the control subjects will be the same as the overlap syndrome subjects.

Phase Two Study:

40 patients in overlap syndrome group recruited during phase one study will be invited to participate in phase two study. The overlap syndrome patients who provide informed consent will be randomized into the two treatment arms (20 subjects in each treatment arm).

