11. RECRUITMENT

The studies will be conducted during wakefulness and sleep in normal subjects, those with COPD and OSA. Males and females (18-79 years) will be studied. Equal numbers of men and women with OSA and controls will be recruited by research staff from the CTF Sleep Laboratory. Subjects will be recruited after they initiate contact in response to IRB approved standard posters, newspaper advertisements, and/or flyers. Subjects who initiate first contact will be followed up with a telephone screening to ensure they qualify for participation in the study. Patients who have indicated they would like to be involved in research to their primary care physician and verbally consented to being contacted for this purpose will be approached directly by a research coordinator. All participants will have an “opt-out” provision to avoid any possibility of coercion. Advertisement for this study will also be placed in appropriate locations in English and Spanish. Finally, if we sometimes have difficulty recruiting people of Hispanic ethnicity, advertisements will also be placed in regions of the community with a high Hispanic population. Recruitment advertisement text previously provided will be utilized for all modes of recruitment mentioned previously. If the provided text is to be changed, each recruitment item will be submitted to IRB for review and reapproval.

A flyer describing the study will also be placed in the waiting room of the UCSD Sleep and Pulmonary Clinic. Subjects will be screened for snoring (historically), body mass index (BMI), and history of COPD.

ResearchMatch will be used to contact prospective participants with IRB approved recruitment message, which is on a separate page labeled “ResearchMatch Message to Potential Participants.”

Spanish translated flyers and advertisements will be submitted after approval of the English documents.

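### Part One has no recording, matching or restriction for smoking or corticosteroid use, so group differences in airway inflammation, serum markers and endothelial function cannot be separated from those exposures if the baseline visit is run as listed

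*Protocol*

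**What the plan says.** Protocol section 9 describes Part One: "The first part is a cross-sectional cohort study comparing subjects with overlap syndrome to those with COPD alone and those with OSA alone". Control of group differences is described in three places.

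- **Matching.** Section 10 says that the control groups are "age and gender matched to the overlap syndrome patients". No other factor is named.
- **Eligibility.** Section 9 says "The exclusion criteria for the control subjects will be the same as the overlap syndrome subjects". Those criteria concern oxygen or positive-pressure use, renal failure, pregnancy, arrhythmia and MRI contraindications. None concerns smoking or steroids.
- **Data collected.** Section 11 says "Subjects will be screened for snoring (historically), body mass index (BMI), and history of COPD". The baseline visit in section 9 is itemised down to individual cytokines, named questionnaires and gargle volumes, but has no smoking history and no medication record.

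On airway inflammation, the baseline visit states "Assessment of upper airway inflammation will be done with a minimally invasive technique, pharyngeal lavage, immediately before and after the sleep study". The secondary endpoints in section 9 include lavage cell counts, EndoPAT and "serum and pharyngeal lavage inflammatory biomarkers (CRP, TNF-alpha, IL-6, P-selectin, ICAM-1)". The baseline text calls the blood marker analyses exploratory.

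Smoking is mentioned once, in section 7: "COPD is also characterized chronic inflammation of upper and lower airways, which was initially triggered by smoking". Inhaled steroids are mentioned once, under Part Two in section 9: "Regular therapy with COPD medications including long-acting anticholinergic medications and inhaled corticosteroids will be continued as advised by the treating pulmonologist".

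**The concern.** In a non-randomised comparison, a confounder can be handled by restriction, by matching, or by recording it and adjusting. The protocol provides none of the three for smoking or corticosteroid use.

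The protocol's own text makes both exposures relevant. It ties smoking to the inflammation that the lavage is meant to characterise, and it describes inhaled steroids as part of regular COPD therapy. Two of the three groups are selected for having COPD and the third is not, so unequal exposure is a foreseeable result of how the groups are formed. Overlap and COPD-only patients may differ too, since only age and gender are matched.

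At stake is aim (b) in section 6, the exploration of mechanisms in overlap syndrome. A difference in lavage cells, a serum marker or EndoPAT could reflect overlap, smoking or treatment. An analysis plan can adjust only for variables that exist, so the choice of what to collect belongs in the protocol.

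**Working it through.** **Step 1: is either exposure controlled anywhere?**

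| Route | Where | What is covered | Smoking or steroids? |
|---|---|---|---|
| Restriction | Sections 9 and 10 | Oxygen/PAP, renal, pregnancy, arrhythmia, MRI | No |
| Matching | Section 10 | Age, gender | No |
| Screening | Section 11 | Snoring, BMI, COPD history | No |
| Baseline items | Section 9 | Imaging, sleep study, blood, urine, EndoPAT, lavage, walk test, questionnaires, cognition, lung function | No |
| Stratified allocation (Part Two) | Section 9 | 1:1 sealed envelopes, no strata stated | No |

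**Step 2: how large could the effect be?** The protocol gives no effect size, SD or exposure prevalence for these endpoints, so there is no figure to reproduce. The following is an illustration on assumed inputs.

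Let exposure prevalence be pA and pB in the two groups. Let exposure shift a marker by d, in units of the SD within exposure strata, and let there be no true disease effect. Then:

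- spurious difference b = (pA − pB) × d
- SE = √{[1 + pA(1 − pA)d²]/nA + [1 + pB(1 − pB)d²]/nB}
- false-positive rate = Φ(b/SE − 1.96) + Φ(−b/SE − 1.96)

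Example: 50% v 30%, d = 0.5, 50 per group. b = 0.20 × 0.5 = 0.10. SE = √[(1.0625 + 1.0525)/50] = 0.206. b/SE = 0.486, and the rate is 7.7%.

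Section 9 gives 150 overlap patients and section 10 gives 50. That is a separate contradiction, so both sizes are shown, with group A as the overlap group. Each cell gives results for d = 0.3 / 0.5 / 0.8.

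| Assumed pA v pB | Spurious difference (SD) | False positives, 50 v 50 (%) | False positives, 150 v 50 (%) |
|---|---|---|---|
| 45% v 35% | 0.03 / 0.05 / 0.08 | 5.3 / 5.7 / 6.6 | 5.4 / 6.0 / 7.4 |
| 50% v 30% | 0.06 / 0.10 / 0.16 | 6.0 / 7.7 / 11.6 | 6.5 / 9.2 / 15.1 |
| 50% v 15% | 0.105 / 0.175 / 0.28 | 8.2 / 13.7 / 26.2 | 9.8 / 18.3 / 37.2 |
| 70% v 10% | 0.18 / 0.30 / 0.48 | 14.5 / 31.3 / 63.0 | 19.5 / 44.1 / 80.9 |

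The bias does not shrink with sample size, so the larger overlap group makes a false result more likely. The model takes one exposure at a time. Smoking and steroids could act in opposite directions, and the net bias could then be smaller.

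**Step 3: Part Two.** Randomisation balances both exposures in expectation. With 20 per arm, an exact binomial calculation gives the chance of a gap of at least 4 patients (20 percentage points) as 0.226 at a prevalence of 30% or 70%, and 0.268 at 50%. That is chance imbalance, not systematic bias.

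**The case against.** The strongest reply is that the protocol is silent on smoking; it does not say that smoking goes unrecorded. The baseline list is not a complete data list: it also omits age, sex and medical history, which matching and eligibility require. Patients come largely from pulmonary and sleep clinics, whose records may hold smoking and drug histories. This stands. A reader might infer that the protocol rules out collecting these data, or that no later analysis could ever remove the confounding. Neither is supported. The conclusion is conditional on the visit being run as listed, and data retrieved from records would allow some adjustment.

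Three further points stand in part.

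- COPD clinic patients are sorted into overlap or COPD-only by the sleep study, so these two groups share a source population. That makes gross imbalance less likely, but does not ensure similar smoking or steroid use.
- Lavage is taken before and after sleep. In the overnight change, an additive and stable exposure effect cancels. This does not help comparisons of lavage levels, serum markers or EndoPAT.
- Adjustment is weakest where imbalance is likely to be greatest. If few OSA-only patients take inhaled steroids (an assumption), steroid use nearly coincides with COPD. Because smoking is named as the trigger of COPD inflammation, adjusting for it against OSA-only may also remove part of the disease effect.

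The choice of covariates can be left to an analysis plan that is not shown, so its absence here is no fault. The collection of the data is a different matter.

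**Conclusion.** The point holds for Part One. As written, the comparisons of lavage, serum marker and EndoPAT endpoints are open to confounding by smoking and corticosteroid use, and the protocol provides no means of handling it.

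The size is unknown from the documents. With 50 per group, the assumed scenarios run from almost no inflation (5.3%) to 63% false positives. The upper end rests on an assumed 60-point gap and a 0.8 SD shift, and should not be read as an estimate.

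The reach is limited. These endpoints are secondary or exploratory. A reader might extend the point to the randomised BiLevel versus nocturnal oxygen comparison, or to RVEDV, the primary endpoint. The first is balanced in expectation, and nothing in the documents shows an effect on the second. The sentence on continuing inhaled steroids belongs to Part Two, so for Part One it shows only that the protocol regards them as regular COPD therapy.

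**What to change.** Add to the baseline visit items in section 9:

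- smoking status (never, former, current) and time since last cigarette;
- pack-years;
- current inhaled or oral corticosteroid use.

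For lavage, serum marker and EndoPAT endpoints, adjust the overlap versus COPD-only comparison for smoking and steroid use. This is the contrast in which adjustment is most informative, because both groups have COPD.

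For contrasts with OSA-only, adjust for or stratify by smoking as a sensitivity analysis. State that steroid use cannot be fully separated from COPD in these contrasts, and that smoking adjustment may remove part of the COPD effect.

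The cost is a few case-report-form questions at a visit that already takes about 12 hours, and slightly wider confidence intervals from the added covariates. No procedure or patient is added.

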Treatment of hypoxemia in COPD alone has been shown to improve mortality. However, treatment of hypercapnia in COPD with nocturnal Bilevel has shown contradictory results. Of note, known OSA was excluded from the bulk of these above cited COPD studies. We postulate that COPD patients with concomitant OSA may be ideal candidates for positive pressure ventilation, since this intervention could treat both hypoxemia and hypercapnia.

Positive airway pressure therapy in overlap syndrome

Overlap syndrome patients are typically hypercapnic at more preserved levels of lung function than those with COPD alone (average forced expiratory volume in one second, FEV1 1.8 vs. 1.0 L). Therefore, overlap syndrome patients are likely to be particularly susceptible to pulmonary artery vasoconstriction due to intermittent hypoxemia and hypercapnia. OSA causes pharyngeal obstruction resulting in intermittent hypercapnia and hypoxemia. Accessory respiratory muscle atonia during REM sleep in patients with underlying COPD commonly leads to hypercapnia. By decreasing hypoxemia and hypercapnia, with resultant reduction of pulmonary artery vasoconstriction, treatment of overlap syndrome at night may well improve RV

(and LV) performance during the daytime. One uncontrolled study showed an improvement in gas exchange and FEV1 with CPAP therapy in overlap syndrome. Another prospective study showed a reduction in mortality and hospitalizations due to COPD exacerbations after CPAP therapy in overlap syndrome. Furthermore, we recently observed in 11,000 patients improved mortality in a dose response relationship with CPAP use in patients with overlap syndrome, although again lack of randomization limits definitive conclusions. To date, no prospective, randomized, controlled study has yet evaluated the effect of BiLevel therapy on clinical outcomes in overlap syndrome.

Rationale for using BiLevel vs. NOT

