Follow-up visits: The first follow-up visit will be done 2 weeks after starting treatment to ensure compliance and determine any discomforts due to treatment. At this visit phlebotomy will be done to take blood samples for venous gas analysis. Subjects will be asked to complete all questionnaires as outlined in the baseline visit. Second follow-up visit will be done 3 months after starting treatment to ensure compliance with treatment and determine any study related discomforts. Subjects will be asked to complete all questionnaires and cognitive function testing as outlined in the baseline visit. The final follow-up visit will be done 6 months after starting study treatment. Throughout the course of the study, regular telephone contact will be maintained by the study staff to ensure adherence to therapy and to address issues as they arise. At this final follow-up visit, all the tests done at baseline visit (except PSG) will be repeated as well as all afore mentioned questionnaires and cognitive function testing. This pilot study will generate preliminary data for a multi-center clinical trial with longer duration of PAP therapy and mortality, hospitalizations or COPD exacerbations as outcomes, if we find encouraging results. If the subject is called for follow-up visits, first follow up visit will require a time commitment of 15-20 minutes (2 week mark of starting treatment) for and the other two follow up visit will require a time commitment of 25-30 minutes (one at the 3-month mark of starting treatment and one final follow up visit). During the course of the 2 week, 3 month and 6 month periods between follow up visits, study staff may contact the patient to ensure adherence to therapy and address issues as they arise. While these phone call encounters may vary in time based on the subject's needs, typically they should require no more than 5-10 minutes of the subject's time.

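### Randomised patients who have a COPD exacerbation are not called back, so the primary 6-month RVEDV is never measured in them and the arms are compared in a subset selected after randomisation

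*Protocol*

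**What the plan says.** Protocol section 9, Part Two, randomises 40 overlap patients 1:1, 20 to BiLevel (with oxygen if needed) and 20 to nocturnal oxygen alone (NOT). It then restricts follow-up: "Only COPD subjects with stable clinical course during the duration of study intervention will be called for follow-up visits". The reason given is "as any COPD exacerbations during the course of study intervention may potentially confound the follow-up study results".

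The paragraph on follow-up visits lists contacts at 2 weeks, 3 months and 6 months. The listed procedures include cardiac MRI only at the last of these: "At this final follow-up visit, all the tests done at baseline visit (except PSG) will be repeated". The same paragraph words attendance as conditional, "If the subject is called for follow-up visits", so the restriction is no stray phrase. Telephone contact does continue: "Throughout the course of the study, regular telephone contact will be maintained by the study staff".

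The endpoints paragraph makes RVEDV by cardiac MRI the primary endpoint, both across the three cross-sectional groups and "following intervention in the overlap syndrome patients in the randomized trial".

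**The concern.** The rule decides who has a primary outcome by something that happens after randomisation. The protocol treats that event as a confounder. A confounder in a randomised comparison would have to precede allocation, whereas an exacerbation during treatment may be a result of it. The protocol takes that possibility seriously. Its background section says: "Another prospective study showed a reduction in mortality and hospitalizations due to COPD exacerbations after CPAP therapy in overlap syndrome". It also names exacerbations among the outcomes of the larger trial that this pilot is meant to inform.

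Three things are at stake:

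- **Validity.** If exacerbation risk differs by arm and is related to RV change, the patients scanned at 6 months are not comparable between arms, and the RVEDV contrast is biased.
- **Precision.** Even with equal risks, a trial of 20 per arm loses primary data by rule.
- **Feasibility.** Aim (c) in section 6 is to establish feasibility. The rule hides how many randomised patients could have completed a 6-month scan.

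Stable clinical course is also left undefined, and no blinding of that judgement is described. Selection therefore depends on opinion as well as on events.

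**Working it through.** **Is there another route to RVEDV?** Section 9 calls only stable patients, schedules the repeat MRI only at 6 months, and defines the primary endpoint by that MRI. No section provides a delayed scan or another source of RVEDV for a patient who exacerbates. A late exacerbator may already have attended at 2 weeks and 3 months, but neither visit includes an MRI. The loss of the primary outcome follows from the text alone.

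**What can be reproduced.** 2 × 20 = 40 agrees with the stated total. The protocol gives no power calculation, SD, dropout rate or exacerbation rate, so the rest is an illustration on assumed inputs.

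**Assumptions.**
- Six-month exacerbation risk in the higher-risk arm: 10–50%.
- Risk ratio between arms: 1 (equal), or 1.7 to 2. The protocol gives no treatment effect on exacerbations. Its relative risk of 1.70 compares overlap with COPD-only patients and is not a treatment effect.
- Correlation ρ between exacerbation liability and RVEDV change: 0.2–0.6, with a larger RVEDV taken as worse.
- No true treatment effect on RVEDV.

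**Scans lost** = 20 × (p_NOT + p_BiLevel).
- Equal risks of 10–20%: 4–8. Equal risks of 30–50%: 12–20.
- Ratio 1.7–2, higher risk 10–20%: 3.0–6.4. Higher risk 30–50%: 9.0–15.9.

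**Difference detectable** (two-sided 5% t-test, 80% power):

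| Patients with RVEDV (NOT / BiLevel) | Detectable difference |
|---|---|
| 20 / 20 | 0.91 SD |
| 14 / 14 (30% risk in each arm) | 1.10 SD |
| 12 / 16 (40% v 20%) | 1.11 SD |
| 12 / 12 (40% in each arm) | 1.20 SD |
| 10 / 10 (50% in each arm) | 1.32 SD |

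**Bias.** Under a bivariate normal model, the mean RVEDV change in non-exacerbators is −ρ·φ(c)/(1−p), where c is the normal quantile at 1−p. The bias is the BiLevel value minus the NOT value.

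- Equal risks: the two terms cancel and the bias is 0.
- 40% on NOT v 20% on BiLevel: φ(0.253)/0.60 = 0.386/0.60 = 0.644, and φ(0.842)/0.80 = 0.280/0.80 = 0.350. The difference is 0.294. Multiplied by ρ = 0.2, 0.4 and 0.6, this gives 0.059, 0.118 and 0.176 SD.
- 50% v 25%, ρ = 0.6: (0.399/0.50 − 0.318/0.75) × 0.6 = (0.798 − 0.424) × 0.6 = 0.2245 SD.
- Range at a ratio of 1.7–2: 0.036–0.2245 SD for a higher risk of 30–50%, and 0.014–0.093 SD for 10–20%.

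The sign is against BiLevel when NOT has more exacerbations, because BiLevel then keeps more of its sicker patients. With the arms swapped, the same sizes favour BiLevel.

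**Scale.** In the worst case, 10 v 15 patients remain. The standard error is √(1/10 + 1/15) = 0.408 SD, so the bias is 0.2245/0.408 = 0.55 standard errors. Against the full-sample standard error, √(1/20 + 1/20) = 0.316 SD, it is 0.71.

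**The case against.** The strongest reply is that the sizes are guesses and the trial is a pilot.

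- **Risk.** The documents support no particular exacerbation risk. At 10–20% the rule costs 3–8 scans and, at a ratio of 1.7–2, biases the contrast by at most about 0.09 SD.
- **Differential risk.** A difference between arms is not documented either. The supporting study concerns CPAP, which the protocol itself distinguishes from BiLevel, and section 7 says that "treatment of hypercapnia in COPD with nocturnal Bilevel has shown contradictory results". At a ratio of 1.25, the bias is only 0.018–0.092 SD even at 30–50% risk.
- **Size.** The worst case is about half a standard error of the comparison actually made.
- **Purpose.** Section 6 frames this part as a feasibility pilot.

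All of this stands as a limit on the illustrated bias, and none of it reaches the defect. The outcome is uncollected at any exacerbation risk above zero. The pilot label softens the consequence but does not remove it. Hypothesis (b) is comparative, the randomised part has a primary endpoint, and section 5 says that a significant improvement would encourage PAP use and that encouraging data would lead to a multi-centre trial. The wish to avoid scans distorted by an acute episode is reasonable, but it concerns when the scan is done, not whether it is done.

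**Conclusion.** The concern holds. As written, the protocol leaves the primary outcome of the randomised part unmeasured after a post-randomisation event that treatment may affect. This is a fault of data collection, so a statistical analysis plan could not repair it.

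That conclusion rests on the text and is firm. The sizes rest on assumed risks, risk ratios and correlations: 3–20 of 40 scans lost over the whole range examined, and a bias from zero (equal risks) to about 0.22 SD (50% v 25%, ρ = 0.6). The documents cannot settle the direction of the bias. It must be fixed before follow-up begins, because missed 6-month scans cannot be obtained later.

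**What to change.** In section 9, Part Two, replace the restricting sentence and its reason with: *All randomised subjects will be called for every follow-up visit, including the 6-month MRI, whatever their exacerbation history. A visit that falls in an active exacerbation is deferred by a prespecified window and then done.* The investigators must fix the window's length in the protocol. In the follow-up paragraph, delete the conditional wording about being called. Record exacerbations and their timing by arm. Compare RVEDV in all randomised subjects by assigned arm, and keep the stable-only comparison as a sensitivity analysis. The change concerns outcome collection, not treatment.

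**Cost.** The visits and scans are already scheduled for the 40 subjects, but the documents give no budget. Relative to the rule as written, about 3–20 more subjects would have the 6-month visit, or 9–20 if the higher risk is 30–50%. Section 20 pays $25 + $100 = $125 for that visit, so 9–20 subjects cost $1,125–2,500. A subject who exacerbates early would also regain the 2-week and 3-month visits at $25 each, or $175 in all. The ceiling is 20 × $175 = $3,500, and the floor is 3 × $125 = $375. Scan costs are additional and are not stated. The downside is somewhat more outcome variability and some deferred scans.
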